- (1) The infarction site after onset of MI is vulnerable due to necrosis, and it is difficult to tolerate increased cardiac stress, which may induce myocardial rupture or papillary muscle rupture. Therefore, considering the safety and the impact of higher incidence of serious adverse events (SAEs) on evaluation of the study device, these patients were excluded.
- (2) Since patients with congenital unicuspid or bicuspid may have a theoretical risk of paravalvular regurgitation and expansion failure of the device, these patients were excluded. Patients with no calcification were also excluded, as the THV may not be properly fixated.
- (3) AS patients complicated with severe aortic valve incompetence are expected to have very poor

- 54 -

- (1) Patient has an evidence of an acute MI within 1 month (30 days) prior to the study procedure. Acute MI is defined as; Q wave MI, or non-Q-wave MI with elevation of creatine kinase MB isoenzyme (CK-MB) or troponin, together with the evidence of myocardial ischemia with at least one of the following findings:
 - Symptoms of ischemia
 - Electrocardiogram (ECG) changes indicative of new ischemia (ST-T changes, left bundle-branch block [LBBB])
 - Imaging evidence of a new loss of viable myocardium or new wall motion abnormality.
- (2) Patient has a congenital unicuspid or bicuspid. Or patient has a non-calcified aortic valve.
- (3) Patient has severe aortic valve incompetence.
- (4) Patient has severe mitral valve incompetence.
- (5) Patient has an evidence of any therapeutic invasive cardiac procedures within 30 days prior to the study procedure. However, implantation of a permanent pacemaker or balloon valvuloplasty for bridging to procedure after a qualifying echocardiography are excluded.
- (6) Patient with planned concomitant surgical or transcatheter ablation for atrial fibrillation.
- (7) Patient has pre-existing prosthetic valve in any position.
- (8) Patient is at a high risk of bleeding, difficult to have appropriate treatment, or unable to receive appropriate anticoagulation or antiplatelet therapy.
 - Leukopenia (white blood cell < 3,000 cells/mm³)
 - Thrombocytopenia (platelet < 50,000 cells/mm³)
 - Bleeding diathesis or coagulopathy
 - Active gastro-intestinal ulceration, or upper gastro-intestinal bleeding within the past 3 months
 - Refuse blood transfusion
 - Receiving anticoagulant and/or antiplatelet medication and can't stop them for the study procedure

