 - Concluded by investigator that appropriate anticoagulation or antiplatelet therapy is difficult for any other reasons
- (9) Patient has untreated clinically significant coronary artery disease requiring revascularization.
- (10) Patient has hemodynamic instability requiring inotropic support or mechanical heart assistance. Patient has respiratory instability requiring mechanical ventilation.
- (11) Patient requires an emergency surgery for any reason.
- (12) Patient has hypertrophic cardiomyopathy with or without obstruction.
- (13) Patient has severe ventricular dysfunction with left ventricular ejection fraction (LVEF) < 20%.
- (14) Patient has echocardiographic evidence of intracardiac mass, thrombus, or vegetation.
- (15) Patient has hypersensitivity to or a known contraindication of heparin and/or aspirin, which cannot be adequately pre-medicated. Patient has a known hypersensitivity to contrast media.
- (16) Patient has hypersensitivities to cobalt, chromium, nickel, molybdenum, titanium, manganese,

- 53 -

- (4) Disruption of blood flow may occur in patients complicated with severe mitral valve incompetence due to released AS by the study procedure.
- (5) Excluded because of the possible impact on proper evaluation of the study device. If pacemaker implantation, and balloon aortic valvuloplasty was performed as a role of bridging before the study procedure, the patient could be included in this clinical trial. However, since the mortality risk after treatment with an implantable cardioverter defibrillator in chronic dialysis patients is significantly high,^[43] patients with implantable cardioverter defibrillator were excluded.
- (6) When surgery for atrial fibrillation is simultaneously given, interpretation of data may be difficult and that affects proper evaluation of the study device. In addition, it has been reported that concomitant procedure with sAVR in chronic dialysis patients was a significant risk factor for periprocedural death^[44], and it was suggested that also in the treatment with EWJ-003 concomitant procedure may be a risk factor for outcome of death. Therefore, from the endurance and safety standpoints, concomitant procedure was excluded. Patients with scheduled coronary revascularization at the same time were excluded by the exclusion criterion (9).
- (7) Excluded because of the possible impact on proper evaluation of the study device.

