9.2 Secondary Endpoints

9.2.1 Secondary safety endpoints

- Composite endpoint: Post-procedure 30 days, 6 months, 1 year, and 2 to 5 years annually
 - Death and stroke
- Single endpoints: Post-procedure 30 days, 6 months, 1 year, and 2 to 5 years annually
 - Death (cardiovascular, non-cardiovascular)
 - MI (periprocedural, spontaneous)
 - Stroke (disabling, non-disabling)
 - Bleeding (life-threatening or disabling, severe, mild)
 - Vascular access site/access-related complications
 - Severe vascular complications
 - Conduction disorder/arrhythmia
 - Conduction disorder requiring new pacemaker implantation
 - Aortic valve re-intervention
 - Coronary obstruction
 - Endocarditis
 - Valve explants
 - Structural valve deterioration
 - Nonstructural valve dysfunction

Table 10-1: Permissible time windows for the tests/observations

Test/observation timing	Baseline ^{a)}	Procedure ^{b)}	Immediately after procedure	Post-procedural follow-up observation		
				Hospital discharge	30 days post-procedure	6 months post-procedure
Reference date (time)	-	Day 0	Up to 72 hours after exiting the operation room	7 days post-procedure or hospital discharge, whichever comes earlier	30 days post-procedure	182 days post-procedure
Permissible time window	Within 60 days pre-procedure	-	-	± 2 days	-7 days/+14 days	± 30 days

^{a)} The 12-lead ECG should be performed within 48 hours prior to entering the operation room, clinical laboratory tests within 14 days prior to the procedure, and coronary angiography and aortofemoral blood vessel evaluation (CT, MRI, or X-ray) within 90 days pre-procedure (see Section 10.2.1 "Baseline"). For the continued access registry, except cases that may be clinically valid, coronary angiography should be performed within 1 year prior to the study procedure.

^{b)} Cardiac catheter test at procedure should be performed immediately before and after the procedure.

Table 10-2: Permissible time windows for the tests/observations

Test/observation timing	Post-procedural follow-up observation				
	1 year post-procedure	2 years post-procedure	3 years post-procedure	4 years post-procedure	5 years post-procedure
Reference date	365 days post-procedure	730 days post-procedure	1095 days post-procedure	1460 days post-procedure	1825 days post-procedure
Permissible time window	± 30 days	± 45 days	± 45 days	± 45 days	± 45 days

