15.1.1.2 As-treated analysis set

A subject population consisting of subjects who were enrolled in this clinical trial and implantation of the study device was initiated is defined as as-treated (AT) analysis set. The time when invasion such as incision was made on the access site is regarded as the start of the study procedure. The primary endpoint and secondary safety and efficacy endpoints will be analyzed in the AT analysis set.

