CCS status of stable angina	
Class 1: No limits to physical activities. Ordinary physical activity does not cause angina, such as walking and climbing stairs. Angina with strenuous or rapid or prolonged exertion at work or recreation.
 
Class 2: Slight limitation of ordinary activity. Angina with walking or climbing stairs rapidly, walking uphill, walking or stair climbing after meals, or in cold, or in wind, or under emotional stress, or only during the 1 to 2 hours after awakening. Or walking more than two blocks on the level and climbing more than two flight of ordinary stairs at a normal pace and in normal conditions.
 
Class 3: Marked limitation of ordinary activity. Angina with walking one or two blocks (80 m - 160 m) on the level and climbing one flight of stairs in normal conditions and at normal pace.
 
Class 4: Inability to carry on any physical activity without discomfort. Anginal symptoms may be present at rest.
	CCS
Cancer	Refers to a condition caused by an uncontrolled division of abnormal cells conditions, and is characterized by invasion into the surrounding tissues, and can progress to distant metastasis. Cancer is classified into benign and malignant, and in this clinical trial, if a subject has a history of malignant cancer, enter as a subject with a history of cancer at baseline in the eCRF.	
Cardiac tamponade	Newly occurred pericardial effusion associated with hemodynamic instability and a clear causal relationship to the study procedure.	VARC-2
Conduction disorder/arrhythmia	
The following data on conduction disorder/arrhythmia will be collected:
 
 Conduction disorder at baseline, paroxysmal or persistent atrial fibrillation/flutter, and permanent pacemaker implantation New or aggravated conduction disorder related to the implanted valve 	VARC-2

Term	Definition	Reference/rationale

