	
 First degree atrioventricular (A-V) block Second degree A-V block (Mobitz type I or II) Third degree A-V block Incomplete right bundle branch block Right bundle branch block Defect intraventricular conduction Left bundle branch block Left anterior hemiblock (LAH) Left posterior hemiblock (LPH) Block requiring permanent pacemaker implantation Persistent or transient advanced A-V block 
When advanced A-V block is observed at every test, it is regarded as persistent.
 
 New permanent pacemaker implantation 
The indications of permanent pacemaker implantation and the number of days after the procedure should be accurately recorded.
 
 Newly found atrial fibrillation/flutter Newly found arrhythmia with hemodynamic instability or requiring treatments 	
Switching to surgery	Refers to cases with switching to open heart surgery by sternotomy due to a procedure-related complication during the study procedure.	VARC-2
Coronary obstruction	During the study procedure or post-procedure newly found prosthetic valve, native cusp, lump lime, or partial or total occlusion at the coronary ostium associated with dissociation in the angiogram or echocardiography findings.	VARC-2
Death	
Death is classified into cardiovascular death or non-cardiovascular death by the cause of death.
 
 Cardiovascular death 
 When applicable to the followings, it is regarded as cardiovascular death: 
 Death directly associated with the heart (e.g.: myocardial infarction, cardiac tamponade, worsened heart failure) Death associated with blood vessels other than the coronary artery (e.g.: neurological event, pulmonary embolism, aortic aneurysm rupture, dissecting aneurysm, and other vascular disease) All study procedure-related deaths, including deaths related to procedural complication and treatments for the procedural complication. All deaths related to the investigational valve, including deaths from structural valve deterioration, non-structural dysfunction, and other valve-related AEs. Sudden death and unwitnessed death Death with unknown cause Non-cardiovascular death 
 It is apparent that the major cause of death is a disease other than the above (e.g.: trauma, cancer, suicide) 	VARC-2

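### New pacemaker implantation is analysed over the whole as-treated set, which may include subjects already paced at baseline, with no at-risk rate beside it

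*Combined protocol and SAP*

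**What the plan says.** **Analysis set.** Section 15.1.1.2 defines the as-treated (AT) set as "A subject population consisting of subjects who were enrolled in this clinical trial and implantation of the study device was initiated" and then states: "The primary endpoint and secondary safety and efficacy endpoints will be analyzed in the AT analysis set". Membership depends on enrolment and the start of the procedure. Baseline rhythm and pacemaker status play no part.

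**Endpoint.** Section 9.2.1 lists "Conduction disorder requiring new pacemaker implantation" as a single endpoint, reported at 30 days, 6 months, 1 year and then yearly to 5 years. It is separate from the broader item "Conduction disorder/arrhythmia".

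**Eligibility.** Exclusion criterion (5) in Section 5.2.2 bars recent therapeutic invasive cardiac procedures but adds that "implantation of a permanent pacemaker or balloon valvuloplasty for bridging to procedure after a qualifying echocardiography are excluded". The rationale shows that this means exempt from the bar: "If pacemaker implantation, and balloon aortic valvuloplasty was performed as a role of bridging before the study procedure, the patient could be included". The same rationale rules out patients with an implantable cardioverter defibrillator, but not those with a pacemaker. No criterion excludes a pacemaker implanted earlier than 30 days before the procedure.

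**Baseline data.** Under conduction disorder/arrhythmia, the Section 30 glossary includes among the data to be collected "Conduction disorder at baseline, paroxysmal or persistent atrial fibrillation/flutter, and permanent pacemaker implantation".

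**Summary method.** Section 15.1.2 plans n, percentage and a 95% CI for binary variables, Kaplan-Meier estimates as needed, and no tests on secondary endpoints. It repeats all analyses for each access approach. It gives no rule for subjects who already have the condition at baseline, and it refers to a separate Statistical Analysis Plan for detail.

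**The concern.** A subject who enters with a permanent pacemaker cannot go on to receive a first one, but under Section 15.1.1.2 still counts in the denominator. In a Kaplan-Meier estimate the same subject stays in the risk set until censoring without ever being able to contribute an event. A reader who takes the reported percentage as the risk of needing a pacemaker after the procedure would then see a figure that is too low, with an upper confidence limit that is also too low.

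This is a device-related safety rate, and the EWJ-003 1-year results go into the study report for the approval application. The information needed to show the at-risk rate is already collected, so leaving it out has no practical justification.

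**Working it through.** **The plan's own figures.** The protocol states no expected rate for new pacemaker implantation, so there is nothing to reproduce for this endpoint. Its one calculated design figure is 81.1% power for the primary endpoint with 24 subjects (Section 4.3). That reproduces with an exact one-sample binomial calculation: success at 6 or fewer deaths out of 24 has exact one-sided alpha 0.0364 at 45% mortality and power 0.8111 at 20%. Nothing below touches it.

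**Inputs**
- N = 30, the target sample size in Section 4.3, taken here as the size of the AT set.
- x = number of subjects with a new pacemaker: not in the documents, assumed.
- k = number of AT subjects already paced at baseline: not in the documents, shown as a range.
- A replacement or upgrade of an existing device is assumed not to count as a new implantation.

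**Formulas**
- Planned rate = x / N.
- At-risk rate = x / (N - k).
- Therefore planned rate = at-risk rate × (N - k) / N. The multiplying factor is the share of subjects at risk; the relative shortfall is k / N.

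**Results** (exact Clopper-Pearson 95% intervals)

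| k already paced | Factor (N-k)/N | x = 3, at-risk rate (95% CI) | x = 5, at-risk rate (95% CI) |
|---|---|---|---|
| 0 (same as planned) | 1.0 | 3/30 = 10.0% (2.1-26.5) | 5/30 = 16.7% (5.6-34.7) |
| 3 | 0.9 | 3/27 = 11.1% (2.4-29.2) | 5/27 = 18.5% (6.3-38.1) |
| 6 | 0.8 | 3/24 = 12.5% (2.7-32.4) | 5/24 = 20.8% (7.1-42.2) |

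With 3 events the upper limit moves by 29.2 - 26.5 = 2.7 points at k = 3 and by 32.4 - 26.5 = 5.9 points at k = 6.

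**By approach.** Section 15.1.2 repeats the analysis for TF, TA and TAo, where denominators are smaller. At the 2:2:1 split predicted in Section 4.3, 30 subjects give 12, 12 and 6. As an assumed example, 2 events among 12 TA subjects is 16.7%; if two of the 12 were already paced it is 2/10 = 20.0% among those at risk. At the minimum of 2 subjects per approach, a single paced subject halves the denominator.

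**The case against.** **The planned figure is legitimate.** New pacemakers per treated subject is a correct description of what happened in the AT set, and Section 9.2.1 does not define the endpoint as incidence among unpaced subjects. No test, performance goal or comparator is attached to it. This stands, and is why the at-risk figure should be added and not substituted.

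**The separate Statistical Analysis Plan may deal with it.** It is not in the available text, and naming an analysis set does not forbid an endpoint-specific denominator within that set. So it cannot be said that no at-risk analysis will be done. But Section 15.1.1.2 states its rule without exception, and that rule governs unless an exception is written.

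**The shift is small against the interval.** At k = 3 the estimate moves 1.1 points inside an interval of 2.1-26.5%. That is fair, and it limits the weight of the point.

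Three stronger readings are tempting and not supported:

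- *That the rate of new atrial fibrillation is understated as well.* "Newly found atrial fibrillation/flutter" appears only as a data item in the glossary; Section 9.2.1 lists just the combined "Conduction disorder/arrhythmia". A subject with atrial fibrillation at baseline can still have an event in that combined endpoint, such as a new atrioventricular or bundle branch block. The dilution arises only if the glossary item is tabulated separately. That could matter, since atrial fibrillation is not itself an exclusion and Section 8.1 anticipates such subjects.
- *That each conduction block should be restricted to subjects without that block at baseline.* The glossary counts worsening of an existing disorder as well as a new one, so a baseline block does not remove a subject from risk, and the restriction would discard events the protocol intends to count.
- *That the pacemaker rate is certainly understated.* With no baseline prevalence in the documents, this is conditional; if nobody is already paced, the two rates coincide.

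**Conclusion.** The point holds for new pacemaker implantation, conditionally. The protocol assigns this endpoint to the whole AT set, admits patients who already have a pacemaker, and specifies no at-risk denominator. Read as an incidence among subjects who could have the event, the planned percentage is low by a relative k/N: 10% if 3 of 30 are already paced, 20% if 6 are, nothing if none are. The percentages in the working rest on an assumed event count, an assumed range for k and an AT set of 30. The relation between the two rates does not depend on the event count.

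The consequence is confined to a descriptive safety rate and its interval. The primary endpoint, its test, alpha and sample size are unaffected. The point merits a change because the better presentation uses data already collected, not because a trial conclusion is in danger.

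**What to change.** Add to Section 15.1.2, and carry into the separate Statistical Analysis Plan, wording to this effect:

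> New permanent pacemaker implantation will also be presented (n, %, 95% CI and any Kaplan-Meier estimate) among AT subjects without a permanent pacemaker at baseline, alongside the figure for all AT subjects. If newly found atrial fibrillation/flutter is tabulated as a separate item, it will likewise also be presented among AT subjects without atrial fibrillation/flutter at baseline.

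Show the number at risk in each column, including in the by-approach tables. Leave the combined conduction disorder/arrhythmia endpoint and the individual blocks on the full AT set.

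The cost is one or two sentences and one extra table column. No new data collection is needed, and the change can be applied to every report through year 5.

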15.1.1.3 Valve implant analysis set

The subject population consisting for all subjects in whom the THV was implanted, and when the subject exited the operation room the implanted THV was maintained is defined as valve implant (VI) analysis set. Subjects for whom the investigational valve was not implanted, including subjects switching to surgery, and TAVI bioprosthetic valve other than the investigational valve was implanted, will not be included in the VI analysis set. As for subjects who received a valve-in-valve procedure, cases with additional investigational valve implantation will be included in the VI analysis set, while cases with additional TAVI bioprosthetic valve other than the investigational valve will be excluded from the VI analysis set. The secondary valve performance endpoints based on the echocardiographic evaluation will be analyzed in the VI analysis set.

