7.2 Study Procedure

In this clinical trial, the investigational valve may be implanted by either TF, TA, or TAO approach. However, TF approach should be the first line of treatment, and when TF approach is difficult to perform, carefully examine the subject's clinical and anatomical characteristics, and then select appropriate access site (TA or TAO approach).

For deployment of the THV, the balloon should be inflated at a nominal volume (see Section 3.2 Table 3-2), and if dilatation at a nominal volume is impossible for medical reasons, the subject should be included in the bailout treatment registry (see Section 7.4 "Bailout Treatment Registry"). In the continued access registry, irrespective of whether the THV was implanted at a nominal volume or not, subjects who received the study procedure will be included in this registry. For preparation of study device, THV rinsing, and detailed implantation procedure, see Attachment 2 "Instructions for Use." In order to ensure and protect the

- 64 -

safety of the subjects, the sponsor should witness all procedures as much as possible and consider to be able to respond to questions about the study device and study procedure.

If severe aortic valve regurgitation is observed after implantation of the THV, a valve-in-valve procedure may be performed. When a valve-in-valve procedure is required, as a general rule, the study device should be used. Since sufficient evidence has not been obtained for the safety and efficacy of the valve-in-valve procedures, a physician who performs implantation should carefully select the size and perform the implantation procedure.

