9.2.3 Secondary valve performance endpoints

- Echocardiography: Post-procedure 30 days, 6 months, 1 year, and 2 to 5 years annually
 - Mean pressure gradient
 - Peak gradient
 - EOA
 - EOAi
 - Aortic valve regurgitation (paravalvular, transvalvular)
 - LVEF
 - Left ventricular mass
 - Left ventricular mass index (LVMI)

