14 SUBJECT TREATMENT DISCONTINUATION

14.1 Subject Treatment Discontinuation

Enrolled subjects will continuously participate in the clinical trial until all follow-up observations specified in the protocol are completed. However, the following subjects should discontinue the trial.

- A subject or the legal representative requests discontinuation of the participation in the clinical trial.
- The principal investigator or subinvestigators judges that continued trial will be a disadvantage for subject's health condition.
- The study procedure has not been started.
- When the subject is exiting the operation room, the investigational valve has not been implanted.
- The investigational valve was removed.
- The subject died.
- Continued participation in the clinical trial was deemed difficult.
- The sponsor requests (continued trial was determined to be a disadvantage in the subjects).

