Structural valve deterioration	
All changes in the functions of the implanted valve resulted from abnormally specific to the valve that may lead to stenosis or regurgitation (exacerbation ≥ 1 of NYHA classification of cardiac performance).
 
Structural valve deterioration includes dysfunction or degradation of the implanted valve, while infection or thrombosis confirmed by re-operation, autopsy, or laboratory tests is not included. Structural deterioration means substantial change in the valve, including wear, damage, calcification, rupture of the cusp, and fraying of the joining thread for the components (e.g.: cusp).
	STS/AATS
Valve thrombosis	All thrombi adhered to the implanted valve or around the valve that obstruct part of the blood flow paths, or interfere with valve functions, or are large enough to be treated. Valve-related thrombus observed at autopsy of a death case that was assessed as unrelated to the study device will not be regarded as valve thrombosis.	VARC-2
Unplanned use of artificial heart-lung machines	Cases for which artificial heart-lung machines were used unplanned for circulatory assistance during study procedure.	VARC-2
Valve implant analysis set	The subject population consisting for all subjects in whom the THV was implanted, and when the subject exited the operation room the implanted THV was maintained is defined as valve implant (VI) analysis set. Subjects for whom the investigational valve was not implanted, including subjects switching to surgery, and TAVI bioprosthetic valve other than the investigational valve was implanted, will not be included in the VI analysis set. As for subjects who received a valve-in-valve procedure, cases with additional investigational valve implantation will be included in the VI analysis set, while cases with additional TAVI bioprosthetic valve other than the investigational valve will be excluded from the VI analysis set.	
Valve-in-valve procedure	Implantation of a new prosthetic valve in the already implanted prosthetic valve during or after the study procedure due to inappropriate implantation position and/or valve function.	VARC-2
Ventricular septal perforation	New ventricular septal perforation newly found during or after the study procedure by angiogram or echocardiography findings.	VARC-2

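### The valve implant set excludes non-study valve-in-valve cases without a time limit, and no rule separates echoes of a second valve from those of the first

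*Combined protocol and SAP*

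**What the plan says.** Section 15.1.1.3 sets the anchor: a subject with the study valve implanted belongs to the VI set if, "when the subject exited the operation room the implanted THV was maintained is defined as valve implant (VI) analysis set". It then treats valve-in-valve by brand. With a second study valve, "cases with additional investigational valve implantation will be included in the VI analysis set"; with another make, "cases with additional TAVI bioprosthetic valve other than the investigational valve will be excluded from the VI analysis set". Neither clause carries a time limit. The glossary repeats the VI definition unchanged.

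The glossary defines valve-in-valve as "Implantation of a new prosthetic valve in the already implanted prosthetic valve during or after the study procedure", with poor position and poor valve function both listed as causes ("during or after the study procedure due to inappropriate implantation position and/or valve function").

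The VI set is used for the valve-performance endpoints in section 9.2.3: "Echocardiography: Post-procedure 30 days, 6 months, 1 year, and 2 to 5 years annually". Section 7.3 requires 5-year follow-up of everyone who leaves the operating room with the valve in place, and section 10.2.8 schedules an echo each year from year 2 to year 5. Section 14.1 lists "The investigational valve was removed" as a ground for discontinuation. It does not list valve-in-valve or re-intervention.

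**The concern.** Membership of an analysis set should not depend on what happens to the subject afterwards. Here a later valve failure, together with the brand chosen to treat it, can decide whether the subject's study-valve echoes are summarised at all. Where the subject is kept, gradients, orifice areas and regurgitation grades measured on a second valve can be reported with those of the first.

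Section 1.1.3 gives confirmation of long-term safety and efficacy over 5 years as a purpose of the trial. Section 1.1.2 records a concern about early calcification and deterioration of bioprostheses in dialysis patients. The echoes read by the core laboratory (section 13.2) are the independent measurement of the valve through year 5, because the event committee in section 13.1 adjudicates only death and stroke, and only to 1 year. In about 30 subjects, one misplaced case is visible.

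**Working it through.** The plan states no figure for this point. Its sample-size calculation concerns 1-year mortality in the as-treated (AT) set and is not involved. The check is therefore a reading of the text followed by an illustration.

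**Step 1: follow one subject through the text.** Suppose the study valve is in place at operating-room exit, its function declines, and a valve-in-valve is done in year 3.

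| Case | Membership of the VI set | Echoes before year 3 | Echoes after year 3 |
|---|---|---|---|
| Non-study valve, exclusion read literally | Removed | Lost from the summaries | Lost from the summaries |
| Non-study valve, exclusion read as index procedure only | Kept | Kept | New valve summarised with study valves |
| Second EWJ-003, either reading | Kept | Kept | New valve summarised with the original valves |

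In the first row the subject meets the opening sentence of 15.1.1.3 and fails its later clause, so the section conflicts with itself. It also means that a 1-year report written before year 3 and a 5-year report written after it would summarise the same 30-day echoes on different sets. In the other two rows the original valve has not been removed, so that ground in 14.1 does not apply and the annual echoes continue unless follow-up ends for another reason.

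**Step 2: what is not affected.** A failing valve that is not re-treated stays in the set with its echoes. A subject whose valve is explanted leaves the trial under 14.1, but the echoes up to explant remain. Aortic valve re-intervention, explant, structural deterioration and nonstructural dysfunction are safety endpoints to year 5 (section 9.2.1). They are analysed in the AT set (section 15.1.1.2), which has no valve-in-valve exclusion.

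**Step 3: illustration of the literal reading.** Inputs: N = 30 from section 4.3, assuming all 30 are implanted and evaluable; f failed valves, of which k receive a non-study valve-in-valve. The documents give neither f nor k, so both are assumed. The VI set shows (f − k)/(N − k) where the whole set would show f/N. Upper limits are two-sided 95% Clopper-Pearson.

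| f | k | VI set as written | All implanted subjects |
|---|---|---|---|
| 1 | 1 | 0/29 = 0% (upper 11.9%) | 1/30 = 3.3% (upper 17.2%) |
| 2 | 1 | 1/29 = 3.4% (upper 17.8%) | 2/30 = 6.7% (upper 22.1%) |
| 3 | 1 | 2/29 = 6.9% (upper 22.8%) | 3/30 = 10.0% (upper 26.5%) |
| 3 | 3 | 0/27 = 0% (upper 12.8%) | 3/30 = 10.0% (upper 26.5%) |

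With k = 0 nothing changes. At the plan's predicted 1-year mortality of 20%, 30 × 0.80 = 24 subjects would remain. One case then gives 0/23 (upper 14.8%) instead of 1/24 = 4.2% (upper 21.1%). Each removed case lowers the proportion by about 3 percentage points at N = 30 and about 4 at N = 24.

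**The case against.** The strongest reply is that the exclusion was meant for the index procedure. The set is defined at operating-room exit, the preceding sentence concerns procedural events such as conversion to surgery, and section 7.2 introduces valve-in-valve as part of the study procedure. The glossary entry is a general event definition, not an analysis-set rule. This reading is reasonable, but the text does not settle it. It also only moves the problem: the subject stays in the set and the later echoes measure another valve.

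Section 7.2 also says "When a valve-in-valve procedure is required, as a general rule, the study device should be used", so non-study cases should be the exception. That stands. It makes removal less likely and mixing of the two valves more likely.

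Third, late failures are reported as safety events to year 5. That stands too, and it limits the harm. It does not correct the echo tables. The structural deterioration definition refers to a worsening of at least one NYHA class, so haemodynamic change without it may not be counted there.

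Fourth, sections 15.1.2 and 15.4 place detailed methods in a separate Statistical Analysis Plan. A rule may exist there; the supplied text contains none. The conflict within 15.1.1.3 and the glossary remains in either case.

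A reader might infer that all valves failing in years 1 to 5 vanish from the results, or that the brand of the second valve decides whether a failure is counted anywhere. Step 2 of the working shows that neither is so. Nor does the plan say that early calcification is expected. It notes a concern, and Table 4-1 lists no structural deterioration in either Japanese bioprosthetic series.

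**Conclusion.** The point holds in a limited form. As written, the VI set can lose a subject, including earlier study-valve echoes, because of a later event. On the narrower reading, or with a second EWJ-003, echoes of two different valves can be summarised together. Either way the gradient, orifice-area and regurgitation summaries are distorted for subjects re-treated by valve-in-valve after leaving the operating room, and for no others.

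The size cannot be taken from the documents, which give no late valve-in-valve rate. The 0/29 against 1/30 rests on one assumed non-study case among 30 evaluable subjects. The direction is probably towards better-looking performance, but that is not certain when a second valve's readings are mixed in, since the documents give no readings after valve-in-valve.

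A reader might also be tempted to state a shift in the year-5 mean gradient. The documents do not support one. They give no gradient for a failing study valve, and the 30% to 60% 5-year survival in section 4.2.1 is from Japanese surgical series, not an assumption for this population. Under the fix below, a failing valve's earlier reading would not enter the year-5 mean in any case.

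Valve performance is a descriptive secondary endpoint without a test, and the primary endpoint uses the AT set. The approval application rests on 1-year data, so re-treatment after that report could not alter it. The wording should still be corrected, because the 5-year echo results are meant to inform on durability.

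**What to change.** In section 15.1.1.3 and the matching glossary entry:

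- State that VI membership is fixed at operating-room exit and does not change afterwards.
- Apply the non-study-valve exclusion only to valves implanted before that point.

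In the analysis of the section 9.2.3 endpoints:

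- Summarise study-valve echoes up to the first aortic valve re-intervention, with either brand, and list later echoes separately.
- At each later visit, report the number of re-intervened subjects with their last echo before re-intervention.

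If the separate Statistical Analysis Plan already has such a rule, the protocol and glossary should be made to agree with it.

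The cost is a few sentences and one extra table row. No new data are needed and patient care does not change. Long-term valve performance may look slightly less favourable.
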